### 6.12.3. Deaths, Other Serious Adverse Events, and Other Notable Adverse Events

#### 6.12.3.1. Adverse Events of Special Interest

Adverse events of special interest include the following:

- Infections (all MedDRA preferred terms in MedDRA SOC “Infections and infestations”)
- myelosuppressive events
  - anemia (hemoglobin <6.5 g/dL),
  - leukopenia (White blood cell [WBC] count <2000 cells/ $\mu$ L),
  - neutropenia (absolute neutrophil count [ANC] <1000 cells/ $\mu$ L),
  - lymphopenia (lymphocyte count <500 cells/ $\mu$ L), and
  - thrombocytopenia (platelet count <75,000/ $\mu$ L)
- thrombocytosis (platelet count >600,000/ $\mu$ L)
- malignancies (except for successfully treated basal or squamous cell skin carcinoma)
- hepatic events including elevations in alanine transaminase (ALT) or aspartate aminotransferase (AST) (>3 times upper limit of normal [ULN]) with total bilirubin (>2 times ULN)
- major adverse cardiovascular events (MACE) which was positively adjudicated
- thrombotic events (such as deep vein thrombosis and pulmonary embolism) which was positively adjudicated

By-patient listing of treatment-emergent adverse events of special interest by AESI category will be developed by disease diagnosis.

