CANDLE typically presents clinically before 6 months of age with fever, repeated attacks of erythematous and violaceous, annular cutaneous plaques, persistent periorbital erythema and edema, finger or toe swelling, hepatomegaly, and variable elevation of acute-phase reactants. Another prominent clinical feature is progressive loss of peripheral fat (lipodystrophy). Patients fail to thrive and lymphadenopathy and hypochromic or normocytic anemia may be seen (Ramot et al. 2011; Torrelo et al. 2010).

In an international collaborative effort, 9 patients with the clinical diagnosis of CANDLE were studied (Liu et al. 2012). Genetic analyses showed that 7 out of 9 patients harbor a genetic mutation in PSMB8 of the immunoproteasome complex (i-proteasome). After the original report of CANDLE in 4 children, a syndrome diagnosed in 3 adult patients with joint contractures, muscle atrophy, microcytic anemia, and panniculitis-induced childhood-onset lipodystrophy was reported under the acronym “JMP” for joint contractures, muscle atrophy, and panniculitis (Garg et al. 2010). Patients with JMP were recently demonstrated to carry a PSMB8 mutation (Agarwal et al. 2010). Five patients were homozygous for the same mutation (T75M). Two patients were heterozygous for the T75M mutation, 1 patient was homozygous for a nonsense PSMB8 mutation (C135X), and 1 patient with clinical CANDLE was PSMB8-mutation negative, suggesting genetic heterogeneity and the possibility of other defects in the i-proteasome or the disease-associated pathway.

CANDLE patients have some overlapping features with JMP patients, including a cutaneous eruption and lipodystrophy (Garg et al. 2010). Although the patients reported as having JMP had more prominent joint contractures and muscle atrophy than patients described as having CANDLE, the detection of the same, and additional, mutations in PSMB8 unifies these disorders as proteasome-associated autoinflammatory syndromes (PRAAS). CANDLE patients present with recurrent febrile episodes, elevated acute-phase reactants, and a characteristic neutrophilic dermatosis with a mononuclear interstitial infiltrate including “immature” neutrophils in the dermis that seems pathognomonic for CANDLE (Torrelo et al. 2015). In fact, 2 patients have been misdiagnosed with acute cutaneous myelogenous leukemia.

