8.1. Discontinuation from Study Treatment

8.1.1. Permanent Discontinuation from Study Treatment

In rare instances, it may be necessary for a patient to permanently discontinue (definitive discontinuation) study intervention. When necessary, a participant may be permanently discontinued from study intervention. If so, the participant will remain in the study and follow procedures for remaining study visits, as shown in the Schedule of Activities (see Section 2).

Possible reasons leading to permanent discontinuation of investigational product:

Laboratory test results

Hepatic event or Liver test abnormality. A patient who is discontinued from investigational product due to a hepatic event or liver test abnormality should have additional hepatic safety data collected via eCRF.

Discontinuation of the investigational product for abnormal liver tests should be considered by the investigator when a patient meets one of the following conditions after consultation with Lilly or its designee:

- ALT or AST $>8 \times$ ULN
- ALT or AST $>5 \times$ ULN for more than 2 weeks after temporary interruption of investigational product
- ALT or AST $>3 \times$ ULN and total bilirubin (TBL) $>2 \times$ ULN or international normalized ratio (INR) >1.5
- ALT or AST $>3 \times$ ULN with the appearance of fatigue, nausea, vomiting, right upper-quadrant pain or tenderness, fever, rash, and/or eosinophilia ($>5\%$)
- Alkaline phosphatase (ALP) $>3 \times$ ULN that is deemed to be of liver origin and drug related
- ALP $>2.5 \times$ ULN and TBL $>2 \times$ ULN
- ALP $>2.5 \times$ ULN with the appearance of fatigue, nausea, vomiting, right quadrant pain or tenderness, fever, rash, and/or eosinophilia ($>5\%$)

Other Laboratory Abnormality Results

Discontinuation of the investigational product should be considered by the investigator when a patient meets one of the following conditions after consultation with Lilly or its designee:

- WBC count <1000 cells/ μ L
- ANC <500 cells/ μ L
- lymphocyte count <200 cells/ μ L
- hemoglobin <6.5 g/dL

Note: If any of the above specific abnormalities are considered a feature of the disease (NNS/CANDLE, SAVI, or AGS) and the investigator determines that it is in the best interest of the patient to continue treatment, patients may continue the investigational product. The reason for the decision will be documented in the medical record after discussion with Lilly or its designee.

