8.1.2. Temporary Discontinuation from Study Treatment

On occasion, the investigator may find it necessary to temporarily interrupt or prematurely permanently discontinue investigational product administration following the occurrence of an AE or an abnormal laboratory finding. Except in cases of emergency, it is recommended that the investigator consult with Lilly or its designee before temporarily interrupting or prematurely permanently discontinuing therapy. Based on investigator discretion, if significant changes from baseline in eGFR are observed, the lab test should be repeated and confirmed on 2 separate occasions and Lilly or its designee must be contacted to discuss and document the appropriate course of action which may include a nephrology evaluation.

As listed in Table JAJE.6, certain situations necessitate a discussion with Lilly or its designee about whether treatment should be continued, either at the same dose or with a dose decrease, or if treatment should be temporarily withheld. Although Table JAJE.6 outlines guidance for certain situations, a discussion with the Sponsor should occur about the best course of action and decisions should be documented. Follow-up- laboratory tests to monitor the abnormal finding should be done promptly and frequently at the discretion of the investigator. The investigator must obtain approval from Lilly or its designee before restarting investigational product that was temporarily interrupted for an AE or for an abnormal laboratory finding.

Table JAJE.6. Guidance on Interruption of Investigational Product

Hold investigational product if the following laboratory test results occur, unless continuation of investigational product is approved by Lilly or its designee with documentation:	If investigational product was stopped, it may be restarted after discussion with Lilly or its designee or when:
WBC count <2,000 cells/ μ L ^a	WBC count \geq 2,000 cells/ μ L
ANC <1,000 cells/ μ L ^a	ANC $>$ 2,000 cells/ μ L (Patients with baseline ANC counts between 1000 and 2000 cells/ μ L may restart investigational product when values return to baseline.)
Lymphocyte count <500 cells/ μ L ^a	Lymphocyte count \geq 500 cells/ μ L
Platelet count <75,000/ μ L ^a	Platelet count $>$ 100,000/ μ L (Patients with baseline platelet counts between 75,000 and 100,000/ μ L may restart investigational product when values return to baseline.)

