Patients with eGFR <60 mL/min/1.73 m ² at assignment of initial dose eGFR <30 mL/min/1.73 m ² ^b	eGFR \geq 40 mL/min/1.73 m ²
Patients with eGFR \geq 60 mL/min/1.73 m ² at assignment of initial dose eGFR <40 mL/min/1.73 m ²	eGFR \geq 50 mL/min/1.73 m ²
ALT or AST $>$ 5 \times ULN or ALT or AST $>$ 3 \times ULN and total bilirubin $>$ 2 \times ULN	ALT and AST return to <2 \times ULN, and investigational product is not considered to be the cause of enzyme elevation.
Hemoglobin <8 g/dL ^a	Hemoglobin \geq 8 g/dL
Symptomatic HZ	All skin lesions have crusted and are resolving
Infection that, in the opinion of the investigator, merits the IP being interrupted	Resolution of infection
Clinical features of VTE (such as deep venous thrombosis or pulmonary embolism) are present ^c	After confirmation that DVT/PE is not present

Abbreviations: ALT = alanine aminotransferase; ANC = absolute neutrophil count; AST = aspartate aminotransferase; DNA = deoxyribonucleic acid; DVT = deep vein thrombosis; eGFR = estimated glomerular filtration rate; HBV = hepatitis B virus; IP = investigational product; PE = pulmonary embolism; ULN = upper limit of normal; VTE = venous thromboembolic event; WBC = white blood cell.

^a Investigational product can be continued if decrease in WBC, ANC, lymphocyte count, platelet count, or hemoglobin is determined to be disease related. The investigator must also consult with Lilly or its designee to continue the investigational product. For patients with hemoglobin values <8 g/dL who were previously evaluated by a hematologist and approved for enrollment by Lilly or its designee, interruption of the investigational drug will be considered if a decrease of >1.5 g/dL from the lowest recorded baseline hemoglobin occurs.

^b For patients with preexisting renal impairment, a lower threshold for interruption may be considered after discussion with Lilly or its designee.

- c Evaluate promptly and institute appropriate treatment. If upon evaluation VTE is ruled out and no other temporary or permanent discontinuation criteria are met, then investigational product may be resumed.

Although temporary interruption of investigational product is not a requirement at times of increased potential risk of VTE (eg, surgery, significant air travel, or other situations involving prolonged immobilization), following appropriate VTE prophylaxis guidelines is recommended to help manage the VTE risk under these circumstances.

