9.2.2. Adverse Events of Special Interest

Adverse events of special interest include the following:

- infections (including TB, HZ, or opportunistic infections),
- myelosuppressive events of anemia, leukopenia, neutropenia, lymphopenia, and thrombocytopenia,
- thrombocytosis (defined as a platelet count $>600,000/\mu\text{L}.$),
- malignancies (except for successfully treated basal or squamous cell skin carcinoma),
- hepatic events (see Section 9.4.6.2),
- major adverse cardiovascular events (MACE) (see Section 10.3.6.1),
- thrombotic events (such as deep vein thrombosis and pulmonary embolism).

Sites will provide details on these AEs as instructed on the eCRF and may be asked for additional description by Lilly.

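### The SAP's anemia AESI cut-off (<6.5 g/dL) follows a different protocol level from the other four cytopenias, without explanation, so a hold-level hemoglobin of 6.5 to <8 g/dL is not an anemia AESI

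*SAP*

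**What the plan says.** Protocol 9.2.2 names "myelosuppressive events of anemia, leukopenia, neutropenia, lymphopenia, and thrombocytopenia" together as AESIs and attaches no cut-off to any of them. SAP 6.12.3.1 supplies the numbers: "anemia (hemoglobin <6.5 g/dL"), WBC <2000, ANC <1000 and lymphocytes <500 cells/µL, and platelets <75,000/µL. It plans a by-patient listing by AESI category, and SAP 6.12 includes AESIs among the outcomes summarized by diagnosis.

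The protocol has two sets of levels for the same counts.

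- **Table JAJE.6 (Protocol 8.1.2), temporary hold.** For hemoglobin the level is "Hemoglobin <8 g/dL". The hold applies "unless continuation of investigational product is approved by Lilly or its designee with documentation". Footnote a allows continuation, after consulting the sponsor, when a fall in any of the five counts is judged disease related. It also has a rule for hemoglobin alone, covering certain patients approved for enrollment with low values: "interruption of the investigational drug will be considered if a decrease of >1.5 g/dL from the lowest recorded baseline hemoglobin occurs".
- **Protocol 8.1.1, permanent discontinuation to be considered.** The levels include "hemoglobin <6.5 g/dL" and "WBC count <1000 cells"/µL, with ANC <500 and lymphocytes <200 cells/µL. There is no platelet level.

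Neither SAP 6.12.3.1 nor the SAP revision history explains the choice of cut-offs.

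**The concern.** Someone reading the AESI listing by category would naturally take the five cytopenia categories to have comparable meaning. For four of them, a value at the hold level is in the category. For anemia, a patient can be low enough for the drug to be held and still be outside it. An empty anemia category could then be read as no hold-level hemoglobin event, which the cut-off does not support.

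Anemia is not an incidental category here. Protocol 3.2 lists decreases in hemoglobin among the most common laboratory changes with baricitinib. The AESI section is also the only SAP safety output that applies a severity cut-off to a hematology value; the graded cut-offs in SAP 6.12.4 are hepatic only.

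**Working it through.** The check is a line-by-line comparison. AESI cut-offs come from SAP 6.12.3.1, hold levels from Table JAJE.6, and discontinuation levels from Protocol 8.1.1.

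| Count | SAP AESI | Table JAJE.6 | Protocol 8.1.1 | AESI ÷ JAJE.6 | AESI ÷ 8.1.1 |
|---|---|---|---|---|---|
| WBC (cells/µL) | <2000 | <2000 | <1000 | 2000/2000 = 1.00 | 2000/1000 = 2.0 |
| ANC (cells/µL) | <1000 | <1000 | <500 | 1000/1000 = 1.00 | 1000/500 = 2.0 |
| Lymphocytes (cells/µL) | <500 | <500 | <200 | 500/500 = 1.00 | 500/200 = 2.5 |
| Platelets (/µL) | <75,000 | <75,000 | none | 75,000/75,000 = 1.00 | none |
| Hemoglobin (g/dL) | <6.5 | <8 | <6.5 | 6.5/8 = 0.81 | 6.5/6.5 = 1.0 |

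Four of the five cut-offs equal the hold level, and none of those four equals an 8.1.1 level. Hemoglobin is the reverse. The ratios only identify which level each cut-off coincides with; they do not measure an effect on results.

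**Band left out.** 8 − 6.5 = 1.5 g/dL, that is, hemoglobin from 6.5 to <8 g/dL.

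**Who can fall in it.** Exclusion criterion 22 starts at hemoglobin <10 g/dL, with an exception for disease-related values. A patient who enters at 10 g/dL or above and falls below 8 has lost more than 10 − 8 = 2 g/dL. That patient meets the hold condition, subject to the exceptions, and is outside the anemia AESI category until the value is below 6.5.

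**Patients under the hemoglobin-only rule in footnote a.** The wording has two readings.

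- If the values <8 g/dL are baseline values, a fall of more than 1.5 from a baseline below 8 puts the trigger below 8 − 1.5 = 6.5 g/dL, which the present cut-off already captures.
- If they are on-study values in patients approved earlier, baseline may be higher. A baseline of 9 g/dL, for example, puts the trigger below 9 − 1.5 = 7.5 g/dL, which reaches into the band.

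The documents do not settle which is meant.

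**Where values in the band still appear.** SAP 6.12.4 lists all hematology values with low/high flags and separately lists treatment-emergent laboratory abnormalities by patient. SAP 6.8.3 summarizes the complete blood count by visit. If an adverse event is reported, it appears in the listings of SAP 6.12.2.1 and, if treatment-emergent, in the summary of SAP 6.12.2.3.

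**The case against.** The strongest reply is that no rule is broken. Protocol 9.2.2 sets no cytopenia cut-offs, and nothing says that AESI levels must equal hold levels. The SAP states no basis for any of the five, so a common basis is inferred from matching numbers. The list does not follow Table JAJE.6 throughout either: its hepatic item names ALT or AST >3 times ULN with bilirubin >2 times ULN, whereas the table also holds at >5 times ULN alone. This stands, and it is why the point cannot be called a contradiction.

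A second reply is that a lower level for anemia may be deliberate. Protocol 3.2 says of CANDLE that "hypochromic or normocytic anemia may be seen", and on one reading of footnote a the figure 8 − 1.5 = 6.5 coincides with the SAP cut-off. That is possible, but no section gives either as the reason. The disease-related exception in footnote a covers the other four counts too, and their cut-offs were not lowered.

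A third reply is that the data are shown elsewhere. This is true and limits the consequence to how a case is labelled. A reader might infer that hold-level anemia would be hidden or lost; the listings in SAP 6.12.4 show otherwise.

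Finally, a new tier would be chosen after the primary and 52-week locks of an open-label study. That is a fair caution, and the tier should be labelled accordingly.

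**Conclusion.** The inconsistency is real, unexplained and minor. The anemia AESI category starts 1.5 g/dL below the hold level, while the other four start at it. The effect is limited to the AESI listing and summary. With about 5 patients planned, it would change the category label of individual cases. How many cannot be computed from the documents, and it may be none.

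This assumes that the bracketed numbers in SAP 6.12.3.1 decide membership of each category, which is their plain reading.

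Two stronger readings are not supported. A reader might infer that <6.5 g/dL is an error or conflicts with the protocol, but no section requires the levels to agree. A reader might also infer that footnote a patients are always captured by the present cut-off; that depends on taking its values <8 g/dL as baseline values. Nothing here says which hemoglobin level is clinically right.

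**What to change.** Reconcile SAP 6.12.3.1 with Table JAJE.6 and Protocol 8.1.1, and state the basis of the five cytopenia cut-offs. If the anemia level is deliberate, give the reason in a sentence.

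Before final database lock, add a <8 g/dL anemia reporting tier, labelled as added after the primary and 52-week locks. Keep <6.5 g/dL as its own tier so that results stay comparable with those analyses. Show each patient's baseline hemoglobin beside the event; a fixed flag at baseline <8 g/dL would depend on one reading of footnote a.

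The cost is a short SAP text change, which Version 5 can carry because it is to be approved before final lock, plus one tier and one column in the AESI output. Anemia AESI counts may rise, and the label tells the reader why. This is a reporting definition only: it changes no hold, restart or discontinuation rule.

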#### **6.12.4. Clinical Laboratory Evaluation**

Observed values (CN and SI) and changes from baseline for hematology, chemistry, urinalysis, and fasting lipids laboratory parameters will be listed separately for each patient, including visit, week of visit, values, units, reference ranges, and flag for low/high results.

By-patient listing of treatment-emergent abnormalities (high, low, abnormal) in laboratory results at any time postbaseline will be developed. Abnormal elevations in hepatic laboratory value will be summarized as follows:

- ALT value  $\geq 3$  X ULN at any postbaseline visit,
- ALT value  $\geq 5$  X ULN at any postbaseline visit,
- ALT value  $\geq 10$  X ULN at any postbaseline visit,
- AST value  $\geq 3$  X ULN at any postbaseline visit,
- AST value  $\geq 5$  X ULN at any postbaseline visit,
- AST value  $\geq 10$  X ULN at any postbaseline visit, and
- ALT value  $\geq 3$  X ULN and total bilirubin  $\geq 2$  X ULN at any postbaseline visit (Hy's rule).

By-patient listing of BK virus test will be developed.

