[18] Have any history of venous thromboembolic event (VTE) (deep vein thrombosis [DVT]/pulmonary embolism [PE]) prior to screening.

[19] Have a serious and/or unstable illness that, in the opinion of the investigator, poses an unacceptable risk for the patient's participation in the study.

[20] Have had any major surgery within 8 weeks prior to screening or will require major surgery during the study that, in the opinion of the investigator in consultation with Lilly or its designee, would pose an unacceptable risk to the patient if participating in the trial.

[21] Have screening laboratory test values outside the reference range that, in the opinion of the investigator, pose an unacceptable risk for the patient's participation in the study.

[22] Have any of the following specific abnormalities on screening laboratory tests (patients with NNS/CANDLE will be confirmed the eligibility again using the most recent laboratory test results prior to Visit 6).

- Aspartate aminotransferase (AST) or alanine aminotransferase (ALT) $>2 \times$ the upper limit of normal (ULN),
- Hemoglobin <10 g/dL (100 g/L),
- Total WBC count <2500 cells/ μ L,
- Neutropenia (absolute neutrophil count [ANC] <1200 cells/ μ L),
- Thrombocytopenia (platelets $<100,000/\mu$ L).

Note: The most recent visit prior to Visit 6 is defined as Visit 4 for patients without a biologic agent wash-out or Visit 5 for patient requiring biologic agent wash-out)

Note: A patient with NNS/CANDLE, SAVI, or AGS condition may be enrolled with any of the above specific abnormalities on laboratory tests if these laboratory abnormalities are considered a feature of the disease. If the laboratory abnormality is a feature of the underlying disease must be evaluated, in conjunction with the investigator, and documented; the investigator must also consult with Lilly or its designee before the patient can be enrolled.

[23] Have an eGFR based on serum creatinine at Visit 1 of <40 mL/min/1.73 m²:

- for patients less than 2 years of age (eGFR based on the Bedside Schwarz 2009 formula),
- for patients between 2 years and 18 years of age inclusive (eGFR based on the Japanese Society for pediatric Nephrology formula),
- for patients greater than 18 years of age (eGFR based on CKD-EPI Creatinine 2009 equation)

[24] Have screening thyroid-stimulating hormone and/or thyroxine values outside of the laboratory's reference range and are assessed, in conjunction with the investigator, to be clinically significant.

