9.4.6.2. Hepatic Safety Monitoring

9.4.6.2.1. Close hepatic monitoring*

Laboratory tests (Appendix 4), including ALT, AST, ALP, TBL, direct bilirubin (D. Bil), GGT, and creatine kinase (CK), should be repeated within 48 to 72 hours to confirm the abnormality and to determine if it is increasing or decreasing, if one or more of these conditions occur:

If a patient with baseline results of ...	develops the following elevations:
ALT or AST $<1.5 \times$ ULN	ALT or AST $\geq 3 \times$ ULN
ALP $<1.5 \times$ ULN	ALP $\geq 2 \times$ ULN
TBL $<1.5 \times$ ULN	TBL $\geq 2 \times$ ULN (except for patients with Gilbert's syndrome)
ALT or AST $\geq 1.5 \times$ ULN	ALT or AST $\geq 2 \times$ baseline
ALP $\geq 1.5 \times$ ULN	ALP $\geq 2 \times$ baseline
TBL $\geq 1.5 \times$ ULN	TBL $\geq 1.5 \times$ baseline (except for patients with Gilbert's syndrome)

Abbreviations: ALP = alkaline phosphatase; ALT = alanine aminotransferase; AST = aspartate aminotransferase;

TBL = total bilirubin; ULN = upper limit of normal.

* All ULN values should be age adjusted (AAULN)

If the abnormality persists or worsens, clinical and laboratory monitoring, and evaluation for possible causes of abnormal liver tests should be initiated by the investigator in consultation with the Lilly-designated medical monitor. At a minimum, this evaluation should include physical examination and a thorough medical history, including symptoms, recent illnesses (eg, heart failure, systemic infection, hypotension, or seizures), recent travel, history of concomitant medications (including over-the-counter), herbal and dietary supplements, history of alcohol drinking and other substance abuse.

Initially, monitoring of symptoms and hepatic biochemical tests should be done at a frequency of 1 to 3 times weekly, based on the patient's clinical condition and hepatic biochemical tests. Subsequently, the frequency of monitoring may be lowered to once every 1 to 2 weeks, if the patient's clinical condition and lab results stabilize. Monitoring of ALT, AST, ALP, and TBL should continue until levels normalize or return to approximate baseline levels. Special care should be taken for pediatric patients to minimize the volume of blood taken during hepatic monitoring.

9.4.6.2.2. *Comprehensive hepatic evaluation**

A comprehensive evaluation should be performed to search for possible causes of liver injury if one or more of these conditions occur:

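### The SAP's Hy's rule row pairs bilirubin with ALT only, while its hepatic AESI and the protocol's discontinuation and interruption criteria use ALT or AST

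*SAP*

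**What the plan says.** SAP 6.12.4 opens its hepatic table with "Abnormal elevations in hepatic laboratory value will be summarized as follows". Seven rows follow: ALT at or above 3, 5 and 10 times ULN, AST at the same three cuts, and one combined row. The combined row takes ALT at or above 3 times ULN with total bilirubin at or above 2 times "X ULN at any postbaseline visit (Hy's rule"). It does not name AST. No row refers to baseline, and no row gives bilirubin by itself.

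The same section also plans listings. One is described as "By-patient listing of treatment-emergent abnormalities (high, low, abnormal) in laboratory results at any time postbaseline will be developed". Another gives observed values, and "changes from baseline for hematology, chemistry, urinalysis, and fasting lipids laboratory parameters will be listed separately for each patient".

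SAP 6.12.3.1 defines the hepatic AESI as "hepatic events including elevations in alanine transaminase (ALT) or aspartate aminotransferase (AST"), with the cuts given as "aspartate aminotransferase (AST) (>3 times upper limit of normal [ULN]) with total bilirubin (>2 times ULN"). Either transaminase qualifies. The AESI output is a by-patient listing of treatment-emergent events.

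In the protocol, Section 8.1.1 (discontinuation) and Table JAJE.6 (interruption) both contain a criterion that pairs ALT or AST above 3 times ULN with total bilirubin above 2 times ULN. Exclusion criterion [22] bars AST or ALT above 2 times ULN, but a patient "may be enrolled with any of the above specific abnormalities on laboratory tests if these laboratory abnormalities are considered a feature of the disease", after documentation and consultation with the sponsor. The hepatic monitoring table in Section 9.4.6.2.1 begins "If a patient with baseline results of" and splits at 1.5 times ULN. Sections 9.4.6.2.2 and 9.4.6.2.3 use the same split.

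**The concern.** A count labelled Hy's rule is one of the first figures a safety reader looks for. In this SAP it rests on a narrower definition than the hepatic AESI one section earlier, and narrower than the criteria on which the protocol acts. Neither document gives a reason for leaving AST out of this row. AST is already tabulated in three rows of the same table; only its pairing with bilirubin is missing. A report could therefore show a hepatic AESI and, in the liver table, no Hy's rule case, with nothing in the table to connect the two.

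A second, smaller matter is how the rows are read. Patients may enter with raised transaminases that belong to their disease, and a row that counts any post-baseline value does not show whether the value is new. The count is correct as defined, but the table alone does not let the reader interpret it.

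**Working it through.** No sample size, power or error rate is involved, and the plan states no figure to reproduce. The check applies each definition to illustrative patients. All values are multiples of ULN and are assumptions, not figures from the documents. Values are taken from one visit, because the row does not say whether ALT and bilirubin must coincide.

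Definitions:
- Hy's rule row (SAP 6.12.4): ALT ≥ 3 and bilirubin ≥ 2.
- AESI laboratory criterion (SAP 6.12.3.1): (ALT > 3 or AST > 3) and bilirubin > 2.
- Close-monitoring rule for ALT or AST (protocol 9.4.6.2.1): value ≥ 3 if baseline < 1.5; value ≥ 2 × baseline if baseline ≥ 1.5.

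| Case | Rows of the SAP table | AESI criterion |
|---|---|---|
| 1. Normal baseline; AST 4, ALT 2.5, bilirubin 2.5 | AST ≥ 3 only | met |
| 2. ALT 3.5 at baseline and unchanged; bilirubin normal | ALT ≥ 3 | not met |
| 3. ALT exactly 3, bilirubin exactly 2 | ALT ≥ 3 and Hy's rule | not met |

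Case 1 is the main point. AST 4 > 3 and bilirubin 2.5 > 2, so the AESI criterion is met. ALT 2.5 < 3, so the Hy's rule row does not count the patient.

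Case 2 shows why baseline is worth displaying. The patient is counted in the ALT ≥ 3 row, but 3.5 is below 2 × 3.5 = 7, so the protocol's close-monitoring rule is not triggered.

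Case 3 shows that the difference between ≥ and > matters only when a value falls exactly on a cut.

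Effect of adding AST: the row becomes (ALT ≥ 3 or AST ≥ 3) and bilirubin ≥ 2. Anything above 3 is also at least 3, and anything above 2 is also at least 2. Every patient who meets the AESI laboratory criterion at one visit is therefore counted in the row, and the AESI wording need not change. Case 1 moves into the row.

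Check on removing patients already above a cut at baseline: take ALT 3.2 at baseline rising to 4.9. The patient leaves the ≥ 3 row (3.2 ≥ 3 at baseline) and does not reach the ≥ 5 row (4.9 < 5). Rows for at least 2 or 3 times baseline would not count the patient either (4.9 / 3.2 = 1.53). A genuine worsening would disappear from the table, whereas the present table counts it under ALT ≥ 3.

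Size: about 5 patients are planned (SAP 5.2) and safety is summarised by disease diagnosis (SAP 6.12). One patient is 1/5 = 20 percentage points overall, 1/2 = 50 in a group of two, and 1/1 = 100 in a group of one.

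**The case against.** The strongest reply is that nothing is hidden. The case 1 patient is counted in the AST ≥ 3 row, appears in the laboratory listings with change from baseline, and should appear in the AESI listing. With about 5 patients, SAP 6.1 makes listings a main tool, and a reader of the listings would see both the AST rise and the bilirubin. This stands. A reader might infer that the plan would miss an AST-led liver case altogether; the documents do not support that. The gap is in one summary row.

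A second reply is that an ALT-only criterion has precedent: the transaminase trigger for extra hepatic data collection in protocol 9.4.6.2.3 uses ALT alone. That is true, but that trigger is not a combined transaminase-and-bilirubin rule. Where the documents do form that combination elsewhere (SAP 6.12.3.1, protocol 8.1.1 and Table JAJE.6), they use either enzyme.

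A third reply is that the AESI output lists treatment-emergent events while the table counts laboratory values, so the two need not match exactly. This also stands, but it does not explain the absence of AST.

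Two further inferences should be resisted. One is that counting elevations regardless of baseline is an error. The protocol's baseline-dependent rules are operational triggers, its discontinuation and interruption criteria use absolute multiples of ULN for ALT and AST, and no section prescribes baseline multiples for tabulation. An unchanged elevation can also be recognised from the change-from-baseline listing. The other is that the AESI inequality should be changed to match the table. It now agrees with the strict inequality in protocol 8.1.1 and Table JAJE.6, and changing it would break that agreement to settle exact ties only.

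**Conclusion.** The point holds as an inconsistency of definition within the SAP. The Hy's rule row can read zero when a patient meets the SAP's own hepatic AESI criterion through AST. The consequence is a summary count that disagrees with the AESI listing and needs explaining; no data are lost and no test is affected, since the study is descriptive. One such patient changes the row by 20 percentage points of 5, or by 50 to 100 points in a disease group of two or one, but the same arithmetic applies to any row in so small a study. The documents give no indication of how likely an AST-led case is, or how likely entry at 3 times ULN or more is under the exception in criterion [22]. The change is desirable rather than essential. Showing baseline beside the counts is an aid to reading the table, not the correction of an error.

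**What to change.** In SAP 6.12.4, define the combined row as ALT or AST ≥ 3 × ULN and total bilirubin ≥ 2 × ULN. Leave the AESI inequality in 6.12.3.1 unchanged. Keep all existing any-post-baseline rows and show beside them each counted patient's baseline category, < 1.5 × ULN or ≥ 1.5 × ULN, which is the protocol's own split in 9.4.6.2.1 to 9.4.6.2.3. Do not drop patients who were already above a cut at baseline.

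The cost is a line of SAP text and minor table programming. SAP Version 5 is to be approved before the final database lock, so there is a place for the change. The final combined row may differ from the one in the earlier interim tables; a footnote can say so. These are reporting definitions only, and no clinical rule in the protocol is touched.
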